9.1.4 Unanticipated Adverse Device Effect (UADE)

Unanticipated Adverse Device Effect (UADE) refers to any serious adverse effect on health or safety or any life-threatening problem or death caused by, or associated with, the Tendyne System, if that effect, problem, or death was not previously identified in nature, severity, or degree of incidence in the CIP, or application (including a supplementary plan or application), or any other unanticipated serious problem associated with a device that relates to the rights, safety, or welfare of subjects.

9.2 Device Deficiency

Device deficiency (DD) is defined as an inadequacy of a medical device related to its identity, quality, durability, reliability, safety or performance, such as malfunction, misuse or use error and inadequate labeling. This includes the failure of the device to meet its performance specifications or otherwise perform as intended.

9.3 Device / Procedure Relationship

Determination of whether there is a reasonable possibility that the device, the implant procedure, or the patient condition (pre-existing condition) caused or contributed to an AE is to be **assessed by the investigator** and recorded on the appropriate eCRF. Additionally, the probability of relationship to the device or procedure should also be categorized. This determination should be based on assessment of temporal relationships, evidence of alternative etiology and

medical/biologic plausibility. Definitions for the determination of device- and/or procedure-relatedness include:

- Not Related:** Exposure to the device/procedure has not occurred (no temporal relationship), or the occurrence of the adverse event is not reasonably related in time, or there is a definite alternative etiology, or it is biologically implausible for the adverse event to be related to the use of the device.
- Possibly Related:** Exposure to the device/procedure has occurred; and it cannot be ruled out that the device/procedure is not responsible for the adverse event.
- Definitely Related:** Exposure to the device/procedure has occurred or the adverse event is related in time; and the device/procedure is definitely responsible for the adverse event.

9.4 Adverse Event / Device Deficiency Reporting

9.4.1 AE Monitoring

The investigator will monitor the occurrence of adverse events for each subject during the course of the study. Event description, date of onset, severity, duration, and relationship to device and/or procedure will be recorded on the appropriate eCRF by the investigator or designee.

For subjects implanted with the Tendyne device who exhibit signs or symptoms suggestive of valve dysfunction, a TTE must be performed. If evidence of valve dysfunction is detected via TTE, a CT (or TEE) must be performed.

For this clinical investigation, all AEs will be collected on each subject from the time of study registration through study completion. A summary of AE reporting requirements is further described in this section and summarized in **Table 4**.

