4.2 Number of Subjects to be Registered

This study will enroll male and female subjects who satisfy the inclusion and exclusion criteria and provide written informed consent. This study will register up to 30 subjects at up to 10 investigational sites in the U.S.

Subjects are enrolled in the study upon signing the informed consent form. Subjects are considered registered in the study upon attempt of the implant procedure.

There is no minimum number of subjects to be registered at any site.

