6 SUBJECT SCREENING

6.1 Screening and Baseline Assessments

Once a patient has signed the IRB approved informed consent form, screening of a subject for possible inclusion in the study may commence. The subject's general medical eligibility must be assessed via interview and medical record review prior to subject registration, all screening and baseline assessments shall be within the windows stipulated in **Table 2**. Standard of care tests that are performed prior to obtaining informed consent can be used to determine eligibility if those tests meet the requirements of this study and are within the screening window.

The following screening/baseline imaging and assessments are to be completed prior to registration:

Images must be captured per the core lab imaging protocols for TEE, TTE, and Cardiac CT. If any imaging is not standard of care, the subject (or subject's legally authorized representative) must provide informed consent prior to obtaining any study imaging.

- TEE and TTE images to be obtained and submitted to the Sponsor **within 60 days prior to registration**. The Echocardiography Core Laboratory will review the images and confirm the subject's MR etiology, MR severity, and LVEF.
- Cardiac CT images to be obtained and submitted to Sponsor **within 120 days prior to registration**. Both the CT core laboratory and the Sponsor will review the cardiac CT images and assess annular calcification, assess subject's anatomical suitability relevant to valve sizing, and to perform procedural planning.
- Subject's coronary artery disease status should be assessed via a routine diagnostic coronary angiogram, if clinically indicated. Any revascularization treatment should be administered prior to subject registration as outlined in the subject eligibility criteria in **Section 5.2**.

Screening/Baseline Assessments within 90 Days Prior to Registration

- Medical history must be obtained, including review of subject's medical records. This review will include history of co-morbidities and co-existing medical conditions; previous cardiovascular and peripheral vascular interventions; symptoms and diagnosis of mitral insufficiency.
- A physical exam including an assessment of subject's cardiac status and sitting vital signs.

- Blood tests performed, including: BNP or NT-proBNP, plasma free hemoglobin, serum creatinine, International Normalized Ratio (INR), Creatine kinase-MB (CK-MB) and Troponin (Type I or T)
- A 12-lead electrocardiogram (ECG)

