7.1 Concomitant Procedures

Pre-procedural planning and assessment of MAC may determine that concomitant mitral annulus valvuloplasty is required to ensure mobility of calcification prior to Tendyne valve implantation. In such cases, standard institutional techniques may be used.

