10.2.4 Analysis Samples

The primary analysis sample will be based on the principle of intention-to-treat (ITT). All statistical analyses in this study will be “intent to treat” with enrolled subjects with attempted device implant included in the analysis. As-treated analysis will also be conducted, which includes subjects with study device remain implanted.

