13.3 Electronic Case Report Form Completion

Primary data collection based on source-documented hospital and/or clinic chart reviews will be performed clearly and accurately by site personnel trained on the CIP and eCRF completion. eCRF data will be collected for all subjects that are enrolled into the study.

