16.2 Risks Associated with Participation in the Clinical Study

As previously described, **Table 3** indicates all anticipated AEs/risks associated with the use of the Tendyne Mitral Valve System. The risk associated with study-required testing and assessments are summarized in **Table 6**. Although routine, these tests and assessments may be performed at greater frequency than standard of care practices.

Table 6. Study Procedure-Related Risks

| Study Procedures | Risks |
|--|---|
| History, Clinical Status, QOL Surveys, 6-Minute Walk & Physical Exam | None, Minimal |
| Laboratory testing | Minimal. Usual risks associated with phlebotomy |
| ECG | None, Minimal |
| Echocardiography: TTE | None, Minimal |
| Echocardiography: TEE | A separate written informed consent process consistent with clinic policies and practices will occur outside of study |
| Hemodynamics | A separate written informed consent process consistent with clinic policies and practices will occur outside of study |
| Computerized tomography angiography (CTA) | A separate written informed consent process consistent with clinic policies and practices will occur outside of study |
| Angiography (LV Ventriculogram) / Hemodynamics | Written informed consent consistent with institutional policy |

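### Adverse event collection starts at the implant attempt, so harms from study-required screening tests done after consent fall outside the stated window

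*Combined protocol and SAP*

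**What the plan says.** Two milestones are separated in section 4.2: "Subjects are enrolled in the study upon signing the informed consent form", whereas "Subjects are considered registered in the study upon attempt of the implant procedure". Section 9.4.1 ties AE collection to the second: "all AEs will be collected on each subject from the time of study registration through study completion".

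The screening work lies between the two. Section 6.1 says "The following screening/baseline imaging and assessments are to be completed prior to registration", and the list covers TEE, TTE, cardiac CT, blood tests and the six-minute walk. Sections 5.1 and 5.2.1 require any eligibility test that is not standard of care to be done after consent. Section 16.2 adds that "these tests and assessments may be performed at greater frequency than standard of care practices".

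In Appendix III the Adverse Events row is blank under Screening/Baseline and first marked under Procedure. The Protocol Deviations row is marked from screening onward.

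Other text is broader. The opening sentence of 9.4.1 has the investigator monitor AEs for each subject during the study. Section 9.4.2 requires all SAEs within 3 calendar days and names no start. Section 13.3 says "eCRF data will be collected for all subjects that are enrolled into the study".

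**The concern.** The plan asks consented people to undergo tests that may go beyond their routine care, and then opens the AE window only after those tests are over. A consented subject who fails screening never enters the window at all. Such harms are foreseeable: section 2.1.2 notes that mitral annular calcification is more common with kidney disease, and section 7.3.3 itself urges care with contrast when renal function is compromised.

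At stake is a complete account of what participation costs subjects, and consistent conduct across up to 10 sites that could each read the start point differently.

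A second, smaller issue is that registration, AE collection and the primary analysis sample all depend on an attempt that is never defined and is worded in several ways.

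**Working it through.** There is no planned figure to reproduce. The main check sets the sections side by side.

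**1. When does the AE window open?**

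| Source | Who or what | Start point |
|---|---|---|
| 9.4.1, collection sentence | all AEs | registration |
| 4.2 | registration | attempt of the implant procedure |
| Appendix III, Adverse Events row | AE recording | Procedure visit; screening blank |
| 9.4.1, opening sentence | each subject | during the study, no date given |
| 9.4.2 and Table 4 | all SAEs | none given |
| 13.3 | eCRF data | all enrolled, so from consent |

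The first three rows agree with one another and exclude screening. The last three are broader, and nothing says which governs before registration. The specific collection rule and the schedule are what a site would follow in practice.

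**2. How long is the uncovered interval?** Section 6.1 allows TEE and TTE up to 60 days before registration, most other assessments up to 90 days, and cardiac CT up to 120 days. For a test done after consent, the uncovered time can therefore reach 60, 90 or 120 days. For a consented subject who is never registered, the window does not open. Standard-of-care tests done before consent are rightly outside the study and are not part of this point.

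**3. How many events?** The documents give no screen-failure count, no screening AE rate and no aborted-case rate. No estimate is possible.

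**4. Does the primary endpoint change?** No. Section 3.1 counts device- or procedure-related SAEs at 30 days post implant. A harm from a screening test is not in that set.

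**5. The secondary point: what is an attempt?** Section 4.2 refers to the implant procedure; section 7.3 to an attempted implant of the device; section 10.2.4 to "enrolled subjects with attempted device implant included in the analysis"; and the Index Procedure definition in Appendix II to the first attempt at device implant. Section 7.1 allows that "concomitant mitral annulus valvuloplasty is required to ensure mobility of calcification prior to Tendyne valve implantation", and section 7.2.1 describes apical access before the Tendyne sheath is inserted. A case abandoned at either step has had an implant procedure begun but could be classed as having no attempted device implant.

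The size can only be illustrated. Assume 24 successes in 30 analysed subjects and k omitted failures, with k from 0 to 2. The success rate among all those taken to the procedure is 24/(30 + k):

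- k = 0: 24/30 = 80.0%
- k = 1: 24/31 = 77.4%, a shift of 2.6 points
- k = 2: 24/32 = 75.0%, a shift of 5.0 points

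Both the 24 and the range for k are assumptions. The calculation applies only to misclassified aborted cases, not to screening harms.

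**The case against.** A reader might infer that these harms escape safety reporting altogether. The documents do not support that. Patients become subjects at consent (5.1), all SAEs go to the sponsor without a registration limit (9.4.2, 16.4), reported SAEs are adjudicated (9.5), and eCRFs exist for every consented subject (13.3). A serious screening injury is arguably reportable already. What remains is that non-serious harms are outside the stated window and that the status of serious ones depends on which sentence a site follows.

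A reader might also infer that access and valvuloplasty precede the attempt, so that the worst procedural outcomes are removed from the analysis. That is not the natural reading. Access is a titled step of the Tendyne procedure (7.2.1), valvuloplasty is called concomitant, Table 3 lists valvuloplasty injuries as anticipated events, Technical Success scores access, and the Procedure column of Appendix III covers time both before and after implant. These features show the intent to count such cases. They do not supply a definition, so the ambiguity stands as a clarification only.

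Nor can one say that screening harms are hidden from the DSMB: what it receives is set by a separate charter that is not in the documents.

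Finally, the study tests no hypothesis and has no pass/fail criterion, and the exact 95% interval for 24/30 runs from 61.4% to 92.3%, so the illustrative shift is small beside the sampling uncertainty. That is fair, and it is why this point rests on safety data completeness and not on bias in the primary estimate.

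**Conclusion.** The point holds for screening. Read as written, section 9.4.1 with section 4.2 and Appendix III leaves harms from study-required tests after consent outside AE collection, for up to 120 days in registered subjects and entirely in consented subjects who never reach an attempt. Sections 9.4.1, 9.4.2, 13.3 and Appendix III are not aligned on the start point. The number of events affected is unknown, and the primary endpoint is untouched.

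The undefined attempt is a real but secondary ambiguity. If cases abandoned before device insertion were left out, the reported success rate could only be flattered; the 0 to 5 point range rests wholly on assumed counts and on the less natural reading of the text.

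**What to change.** In section 9.4.1 and Appendix III, collect AEs related to study-required tests, and all SAEs, from consent, and keep collection of all other AEs from registration. Mark the Adverse Events row at Screening/Baseline, and state the same start point in section 9.4.2. Since section 9.3 asks only about the device, the implant procedure and the patient's condition, the AE form also needs a relatedness option for study-required tests.

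As a secondary clarification, give one definition of the attempt and use it in sections 4.2, 7.3 and 10.2.4 and in the Index Procedure entry of Appendix II. It should expressly include access and concomitant valvuloplasty, so that a case abandoned before device insertion is registered, has its AEs collected and stays in the ITT sample as a failure. The exact anchor moment is for the sponsor to choose; a single stated one is what matters.

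The cost is protocol wording and a few forms, since eCRFs already cover all enrolled subjects. The downside is slightly more data entry and possibly a slightly lower reported success rate.

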9.4.2 SAE Reporting to Sponsor and IRB

SAEs may be reported by the subject, observed by the investigator, or documented in medical records and must be reported to the Sponsor on the Adverse Event eCRF. Additional information related to previously reported SAEs should be updated within the eCRF as soon as the information has been reviewed and verified by the investigator.

The investigator should report all SAEs to the Sponsor as soon as possible but no later than 3 calendar days from the day the study personnel became aware of the event or as per the investigational site's local requirements, if the requirement is more stringent than those outlined.

The investigator will further report the SAE to the local IRB according to the institution's IRB reporting requirements.

9.4.3 UADE Reporting to Sponsor and IRB

Tendyne Holdings, Inc., requires the investigator to report any UADE to the sponsor within 3 calendar days of the investigator's knowledge of the event, unless local requirements are more stringent, and to the IRB per requirements.

The Sponsor is required to report the findings of the investigation of any UADE to the FDA and the IRB as soon as possible, but in no event later than 10 working days after knowledge of the event.

9.4.4 Device Deficiency

The investigator should report all device deficiencies related to the Tendyne device to the Sponsor as soon as possible but no later than three (3) calendar days from the day the study personnel becomes aware of the event or as per the investigative site's local requirements if the requirement is more stringent than those outlined. Device deficiencies should be reported to the IRB per the investigative site's local requirements.

The device, if not successfully implanted in the subject, should be returned to Tendyne Holdings, Inc.

9.4.5 Investigational Site AE Reporting Requirements to Sponsor

Investigators are responsible for preparation and submission to the Sponsor of all reportable AEs and DDs identified in the CIP. Adverse event reporting requirements are included in **Table 4**. All reports are subject to inspection and to the retention requirements described in **Section 13.4.1 Investigator Records**.

Table 4. Investigational Site AE Reporting Requirements to Sponsor

| Event | Investigational Site | Reporting timelines |
|-------------------|----------------------|--|
| AE | All Sites | AEs (not including normal or expected post-operative sequelae) must be reported as soon as possible after study personnel becoming aware of the event or as per the investigative site's local requirements, if the requirement is more stringent than those outlined. |
| SAE | All Sites | SAEs must be reported no later than 3 calendar days from the day the study personnel became aware of the event or as per the investigative site's local requirements, if the requirement is more stringent than those outlined. |
| UADE | All Sites | UADEs must be reported no later than 3 calendar days from the day the study personnel became aware of the event or as per the investigative site's local requirements, if the requirement is more stringent than those outlined. |
| Device Deficiency | All Sites | DDs must be reported no later than 3 calendar days from the day the study personnel became aware of the event or as per the investigative site's local requirements, if the requirement is more stringent than those outlined. |

9.4.6 UADE Reporting to FDA by the Sponsor

The Sponsor will report UADEs to the FDA per IDE regulations (21 CFR 812.150(b)(1)).

9.5 Adjudication of AEs

All SAEs and device or procedure related AEs reported during the study will be reviewed and adjudicated by the CEC. Once adjudicated, final reporting of adverse events will be based upon

CEC adjudication. Refer to section **12.11.3 Clinical Events Committee** for the CEC's role and responsibility.

10 STATISTICAL METHODS

10.1 Sample Size Considerations

This is a feasibility study and no formal statistical hypotheses are to be tested for any of the study endpoints. Data collected from this study will provide preliminary device safety and effectiveness data for the use of the Tendyne Mitral Valve System in subjects with mitral regurgitation and mitral annular calcification. Descriptive statistics will be reported for the study data primarily. Inferential statistical analysis will be conducted in an exploratory manner. The sample size for this study is planned to be up to 30 at up to 10 investigational sites.

Statistical methods for the study are outlined below. Additional details will be provided in a Statistical Analysis Plan (SAP).

10.2 Data Analysis Plan

10.2.1 General Principles

All statistical analyses will be performed using Statistical Analysis System (SAS) for Windows (version 9.4, SAS Institute Inc. Cary, NC) or other widely accepted statistical or graphical software.

Descriptive statistics will be used to present the data and to summarize the results. Discrete variables will be presented using frequency distributions and cross tabulations. Continuous variables will be summarized by presenting the number of observations (N), mean, standard deviation, median, minimum, and maximum values.

In general, data for all study subjects combined will be presented. The primary analysis for all baseline characteristics and study outcomes will include all available data for all enrolled subjects. Individual data will be presented in subject listings.

Summaries of the following endpoints present the number and percentage of unique subjects with an event, unless specified otherwise: protocol deviations; subject status; study medications; adverse events. Thus, multiple occurrences of the same event are counted only once per subject, unless specified otherwise.

10.2.2 Subject Disposition

The number and percentage of subjects screened, screen failure, enrolled, treated, and completed will be summarized. Screen failure percentage is calculated from number of screened subjects and other percentages are calculated among number of enrolled subjects. A subject will be considered enrolled once they have signed the study patient informed consent form. Subjects who discontinue from the study will be summarized with reason and listed by their primary reason for discontinuation.

10.2.3 Study Conduct

Protocol deviations from the investigation plan will be summarized by deviation type as well as total. Protocol deviations by investigational site will also be provided.

10.2.4 Analysis Samples

The primary analysis sample will be based on the principle of intention-to-treat (ITT). All statistical analyses in this study will be “intent to treat” with enrolled subjects with attempted device implant included in the analysis. As-treated analysis will also be conducted, which includes subjects with study device remain implanted.

10.2.5 Analysis of Population Demographics, Baseline and Procedural Characteristics

Descriptive statistics will be summarized for baseline demographics, medical history, baseline disease characteristics, echocardiography core laboratory data, and procedural characteristics.

